Mbale regional referral and teaching hospital is a busy center in Eastern Uganda with a catchment population of over 4-5 million people. Based on the annual hospital medical records, over 10,000 births occur annually with a caesarean section rate of 35%; about 12% of these operations are due to obstructed labour.

Study population

Eligibility criteria:

Inclusion Criteria:

We will include patients with OL carrying singleton, term pregnancies (≥ 37 weeks of gestation) in cephalic presentation.

Exclusion Criteria:

We will exclude patients with other obstetric emergencies such as antepartum haemorrhage, preeclampsia and eclampsia (defined as elevated blood pressure of at least 140/90 mm Hg, urine protein of at least 2+, any of the danger signs and fits), premature rupture of membranes and intrauterine fetal death. Patients with comorbidities such as diabetes mellitus, sickle cell disease, renal disease, liver disease and heart disease. We will also exclude those patients with hypokalaemia (148 mmol/L) and alkalosis (bicarbonate >22 mmol/L) because they are more likely to develop adverse drug reactions.

Study procedures

A research team member will inform all patients and their attendants while in the waiting/admission area about the ongoing study as part of the routine health education talks in the unit. Mothers that express no further interest in participating in the study will be noted and not approached again about the same.

On the other hand, those that express interest in knowing more about the study will be approached by a study team member once a diagnosis of obstructed labour is confirmed by the attending physician. The mother will be given more information about the study and a verbal consent will be obtained using a pre-written script in their local language following the short verbal consent in **Appendix 2**. She will also be informed that the research midwife will approach her after the birth to seek formal consent to the use of the data and specimens collected during labour.

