After getting consent from the mother, the research midwife will take the next sequentially labelled study drug package and administer its contents to the consented eligible participant. At baseline, five milliliters of maternal venous blood will be collected: 2 mls in an Ethylenediaminetetraacetic acid (EDTA) vacutainer for a full blood count, and 3 mls in a general vacutainer (red top) for electrolytes, renal function tests, liver function tests and for grouping and cross matching. Ten milliliters of fresh urine will also be collected in a sterile container for analysis. All the specimens will be analysed using the RAPID Point® 500e Blood Gas System which is stationed in the surgical HDU, a short distance away from the labour ward. Lactate in amniotic fluid will be measured at the bedside using a hand-held Lactate Pro2 device (Arkray Factory,

Japan). After administration of the study drug, all the participants will be actively monitored by a research midwife up to 24 hours in order to identify any adverse effects. The research midwife will also use an electronic interviewer administered questionnaire to collect sociodemographic and clinical information from the participant at recruitment and during their stay in the hospital up to 14 days postpartum. Details of the study procedures are in the study flow diagram, figure 1.

[figure not shown]

Figure 1: Study flow diagram for the proposed procedures

Sample size estimation and sampling

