Randomisation: A sequence of random numbers will be generated by an independent biostatistician using an online randomization service at www.sealedenvelope.com in permuted block sizes of four, six and eight. An independent, off-site pharmacist will prepare and consecutively number identical study packages using

the generated random numbers. This will ensure that the allocation is concealed. At the study site, after gaining consent, the research midwife will take the next sequentially labeled study drug package and administer its contents to the eligible participant. Therefore, both the participants and data collectors will remain blinded throughout the study.

Intervention/ Comparator: Eligible participants will be randomly assigned to receive 100 mls (8.4g), 150 mls (12.6g) and 200 mls (16.8g) of 8.4% sodium bicarbonate solution, or placebo (50 mls of NS 0.9%) in a ratio of 1:1:1:1. The study drug (Sodium Bicarbonate 8.4% and Normal Saline 0.9%) will be contained in identical 25 mL glass vials (Neon Laboratories Ltd, Mumbai, India), administered intravenously as a single bolus dose. Since the average waiting time for CS in our labour ward is approximately 110 minutes [11], there will be no need for a repeat dose.

In addition, all patients will receive the available Ministry of Health recommended standard preoperative care for all patients with OL which includes antibiotic prophylaxis, intravenous fluid replacement (1.5 L of normal saline), bladder drainage and lying in left-lateral position as they are being prepared for caesarean section [23]. Details in flow diagram 1.

Data collection

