Our research assistants will be qualified midwives with training in data collection, using dedicated password protected android devices. We will also review relevant health facility records such as antenatal care cards, case notes/file, the maternity and theatre registers. Laboratory parameters including lactate will be measured at baseline, and every thirty minutes after study drug administration until delivery to obtain samples for lactate measurement in umbilical cord blood and the myometrium. The participants will be followed for 7 days postnatal to ascertain the secondary perinatal outcomes and for 14 days postpartum to determine the secondary maternal outcomes. In the first 24 hours after study drug administration, the participants will be closely monitored to identify any drug reactions/adverse events. After administration of the study drug, all the participants will be actively monitored by a research midwife up to 24 hours. The women will be examined and asked directly about the presence of side effects.

Sample collection quality control

Qualified and well-trained research midwives will draw five millilitres (ml) of blood by venipuncture at the antecubital fossa of the non- dominant arm from each participant using a five millilitres syringe. After removing the epidermal needle and the tops of the vacutainers, two millilitres will be emptied into a purple top vacutainer for a full blood count, blood grouping and cross-matching as part of the standard preoperative preparation for all patients with obstructed labour in the hospital. The remaining three millilitres will be emptied into a red top vacutainer for blood chemistries including electrolytes, these are not part of the routine preoperative preparation for patients before caesarean section. Each blood sample will be transported to the laboratory in an ice-cooled container within 30 minutes of collection. Urine samples: Mid-stream urine, ten millimeters will be collected in sterile urine container from the mothers. We will monitor strict adherence to the standard operating procedures for collecting and handling participant samples through ongoing training and spot checks.

Cord blood collection

After the baby is born, the midwife will double clamp and cut the umbilical cord. Cleanse a 4" - 6" area of the umbilical cord with alcohol to remove maternal blood and contaminants (before the delivery of the placenta, if possible). Then blood will be drawn from the cord with a needle.

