Ethical approval will be sought from the Busitema University Research and Ethics Committee (REC), and the Uganda National Council for Science and Technology (UNCST). We shall also seek ethical clearance from the University of Bergen in Norway, since it is a requirement for our collaborators. Administrative clearance to conduct the study will be obtained from the Mbale Hospital Research and Ethics Committee. The Ministry of Health and hospital protocols will be followed in management of emergencies such as neonatal resuscitation during the study [13].

Informed consent will be obtained in two steps as suggested in the differed consent pathway for intrapartum research [14]. In step one, a research team member will inform all patients and their attendants while in the waiting/admission area about the ongoing study. This will be done by the staff on BUHHS-2024-164_Protocol_SoBicOL-II Study_V1.3_10 September 2025_Page 12 of 25

duty as part of the routine general health education talks before a diagnosis of active labour or even obstruction is made by the attending physician. Those who will express interest in knowing more about the study will be taken through the process of obtaining a short verbal consent if they become eligible (Appendix 3). We will keep an inventory of those that decline to participate at this stage, they will not be approached again and no data will be obtained regarding their births or outcomes. Once eligible, women will be informed about the study and verbal consent obtained using a pre-written script in their local language. Those who accept to be in the study will be administered the medication, whilst those who decline or are in any way unsure will not be included. In step two, after delivery in the postpartum period, the participant will be visited by a member of the research staff for the formal informed consent process. From past experience in this same labour ward this might be the scenario for most of the participants. In the case of illiterate participants, an independent witness will also be asked to witness the consent process and sign the consent form besides the participant's thumb print. Pregnant women between 16 - 18 years of age will be included as emancipated minors, who can give a valid informed consent as per the national guidelines [15].

Budget

Budget in USD	Unit price	No of units	Frequency	Total	Justification
Personnel					
Research Assistants	500	4	12	24,000	To offer 24-hour coverage, in the recruitment phase

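### The potassium and bicarbonate safety exclusions have no visible step at which the result is read before the numbered package is taken

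*Combined protocol and SAP*

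**What the plan says.** All places are in the combined protocol and SAP.

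- **Exclusion Criteria.** Women are excluded for hypokalaemia and for "alkalosis (bicarbonate >22 mmol/L) because they are more likely to develop adverse drug reactions". The figure printed beside hypokalaemia looks damaged in the extracted text and is not used here.
- **Study procedures.** The approach for verbal consent follows the physician's diagnosis of obstructed labour. Then: "After getting consent from the mother, the research midwife will take the next sequentially labelled study drug package and administer its contents". The baseline blood draw, including the electrolyte tube, is described after that sentence.
- **Randomisation.** The order is the same: "after gaining consent, the research midwife will take the next sequentially labeled study drug package and administer its contents to the eligible participant".
- **Ethics and consent process.** "Those who accept to be in the study will be administered the medication". The sentence just before it reads: "Once eligible, women will be informed about the study and verbal consent obtained using a pre-written script".
- **Table 1.** Electrolytes and plasma bicarbonate are first measured at Baseline (0). There is no screening column.
- **Sample collection quality control.** The red-top tube is for "blood chemistries including electrolytes, these are not part of the routine preoperative preparation for patients before caesarean section". Also: "Each blood sample will be transported to the laboratory in an ice-cooled container within 30 minutes of collection".
- **Quality control.** All required blood tests are to be done at the bedside on the RAPIDPoint analyser, with a second analyser as backup. Study procedures places the RAPIDPoint in the surgical HDU, near the labour ward.
- **Appendix 1.** Section D (baseline laboratory results) has rows for pH, blood gases and lactate. Section E (study drug administration) follows. No eligibility checklist is visible.

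**The concern.** A laboratory exclusion protects participants only if the result is known before treatment is assigned. Here the approach is triggered by a clinical diagnosis, the deciding tests are not routine, and the text moves from consent to the drug package without mentioning a result. Staff who follow the text could allocate and dose a woman who meets an exclusion that the protocol itself justifies on safety grounds.

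There is also a question for the analysis. Packages are pre-numbered from the random sequence, so taking one is the act of allocation. If a disqualifying result arrives later, the woman is already randomised. The Data analysis plan states intention to treat but does not say how such a woman is to be handled. Without a rule, the decision would be made case by case.

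**Working it through.** The point turns on the order of steps, so the check is a comparison of sections.

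1. **What must be known before allocation?** Potassium and bicarbonate (Exclusion Criteria).
2. **Where do these values come from?** The only described sources are the baseline draw in Study procedures and the Baseline (0) column of Table 1. Since the electrolytes are stated not to be routine preoperative tests, a result would not normally exist before study entry.
3. **When is the package taken?** Study procedures and Randomisation both go from consent to package to administration. The Ethics section goes from acceptance to medication. None of the three places a result in between.
4. **Can eligibility precede consent?** The Ethics section says women are consented once eligible. For the laboratory criteria, that would need a non-routine study sample before consent, and no visible text provides for one. The Ethics sequence and the source of the values therefore conflict.
5. **Which result would decide?** Three routes are described: bedside (Table 1 for bicarbonate, and Quality control), an analyser in the surgical HDU (Study procedures), and transport to a laboratory (Sample collection quality control). The last allows up to 30 minutes before analysis begins. That equals the whole interval from baseline to the first post-dose measurement in Table 1, so the choice of route affects whether a check before dosing is practical.
6. **Where would the check be recorded?** Section D of Appendix 1 has no potassium row. Bicarbonate might be entered under blood gases but is not named.

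**Scale.** Planned recruitment is 280 + 192 = 472, which is 472 / 4 = 118 per arm. The three bicarbonate arms hold 3 × 118 = 354. All 472 pass through the sequence as written. The number who would meet an exclusion is 472 × p, or 354 × p on active drug, where p is the share of entrants with a disqualifying result. The documents do not give p. The earlier trial's 61% acidotic (hence 39% not) is defined by lactate above 4.8 mmol/L, so it cannot stand in for bicarbonate above 22 mmol/L or for low potassium.

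**The case against.** The strongest reply is that the flow diagrams are missing. Study procedures and the Intervention paragraph both refer to Figure 1 for details, and Figure 2 covers participants from screening to analysis. Either may show a laboratory check before randomisation. This stands. It limits the point to the visible text and lowers confidence, although a check shown only in a figure would still leave three sections giving a different order.

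Second, dosing is limited to eligible women: the midwife is to "take the next sequentially labelled study drug package and administer its contents to the consented eligible participant". This shows intent and is fairly credited. It does not say who reads the result, when, or where it is written down.

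Third, Table 1 describes a 5 mL venous sample as standard care, and the 5 mL sample in Study procedures includes electrolytes. In Table 1, however, that comment sits with creatinine, liver tests and blood count. It does not cover the electrolyte or bicarbonate rows, and Sample collection quality control says the opposite of the chemistries.

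Fourth, Quality control describes bedside testing with a short turnaround, using 100 microlitres of blood. This shows that a check is feasible. It does not require one.

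A reader might go further and infer that the baseline sample is taken after the bolus, which would bias change in pH from baseline. The documents do not support that. Data collection separates baseline from the half-hourly samples after the drug, Table 1 labels the draw time 0, and section D of the form precedes section E. The order of sentences in Study procedures is not evidence of the order in time.

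**Conclusion.** The point holds as a gap in the written procedure. Two stated safety exclusions depend on non-routine results, and no visible step makes those results available and recorded before allocation. The statement that eligibility precedes consent, the three sample routes and the missing form fields are inconsistencies in the same chain. This should be fixed; confidence is moderate because Figures 1 and 2 could not be seen.

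The size is the reach of the procedure: 472 women, 354 of them assigned to active drug. Three further inferences are not supported:

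- **A count of ineligible women randomised.** The documents give no prevalence for either exclusion, so any such number would rest on an invented percentage.
- **A breach of intention to treat.** No text says women are removed after randomisation. The plan is silent on how to handle them, which is a lesser fault.
- **Sodium or pH as eligibility criteria.** The exclusion list as shown names neither.

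The conclusion assumes that non-routine electrolytes are not normally available before study entry. That follows from the protocol's own description but is nowhere stated outright.

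**What to change.** Reconcile Exclusion Criteria, Study procedures, Table 1, Randomisation, Sample collection quality control, the Ethics section and Appendix 1, and align them with Figures 1 and 2:

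- State when the time-0 sample is drawn relative to verbal consent. Require that it is run, and the results for the analytes named in Exclusion Criteria recorded, before the next numbered package is taken.
- Name the analyser result that decides eligibility, including when the backup device is in use, and resolve the bedside, HDU and laboratory descriptions.
- Add potassium and bicarbonate fields and an eligibility confirmation to Appendix 1, ahead of section E.
- State that allocation occurs when the package is taken. Count women who meet an exclusion before that point as screen failures. Keep any woman found ineligible after allocation in the intention-to-treat set, and report how many there were.

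The thresholds, and whether any further analyte should exclude, remain with the investigators.

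The cost is protocol wording, a few form fields and a wait for a result that is already scheduled. The wait is a real drawback: the sample size section reports that delivery often comes less than 30 minutes after baseline, and the documents give no analyser turnaround in minutes. The investigators should confirm that the chosen route is quick enough in their unit.

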Obstructed labor is a major problem that accounts for 22% of maternal deaths and 70% of perinatal deaths due to intrapartum asphyxia in low resource settings [4]. In Uganda, half of the 26,000 perinatal deaths audited and reported in 2021/2022 were due to intrapartum birth asphyxia [5]. The maternal and fetal harm of OL comes from intrapartum asphyxia, characterized by accumulation of hydrogen ions that cross the placental barrier to cause fetal acidosis. Acidosis causes failure of basic cellular functions resulting into cell death, especially if it remains uncorrected for an extended period. In a recent RCT, we found that 61% of 477 women with OL were acidotic (lactate >4.8 mmol/L), with a median capillary blood lactate level of 6.9 (3.4–13) mmol/L. In Mbale hospital, perinatal mortality rate is twice the national average of 48 per 1,000 total births [6]. In the Sodium Bicarbonate in Obstructed Labour (SoBicOL) trial, 34% of the newborns had an Apgar score of less than seven, and 12% resulted in early neonatal deaths despite being resuscitated [7]. At two years of age, two thirds of the children born in this cohort had a neurodevelopmental delay [8]. These adverse outcomes may be averted by correcting the metabolic acidosis in obstructed.

Currently, preoperative intravenous fluid infusion (1.5L of normal saline) is a component of the standard preoperative care for all women with OL [9]. Although this practice is adequate to correct electrolyte imbalances and dehydration in most women, it may not be sufficient to reverse the metabolic acidosis. In the SoBicOL trial [7], a single dose of 4.2g was insufficient to achieve significant changes in maternal or neonatal lactate levels in comparison to a placebo. We postulate that our choice of a single dose regimen was too conservative, and only one measurement for the primary outcome at one hour was not ideal. The effect of sodium bicarbonate on maternal blood lactate was only noticeable more than one hour after the intervention. Currently, it is not known if a higher dose of bicarbonate would reverse the acidosis and achieve clinical benefits for the mother and baby.

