neonatal deaths despite being resuscitated. A potential way of improving maternal and perinatal outcomes among women with OL would be to buffer the excess lactic acid with sodium bicarbonate, achieving intrauterine resuscitation whilst awaiting an emergency cesarean section. However, in this situation, there is inadequate time (or staff) to correct the acidosis through careful titration of the bicarbonate infusion. A universal safe and effective dose would therefore facilitate its use. In our previous RCT, a single dose of 4.2g was insufficient to achieve changes in maternal or neonatal lactate levels. It is not known if a higher dose of bicarbonate would reverse the acidosis and achieve clinical benefits for the mother and baby. Therefore, we propose to undertake a placebo-controlled, dose-ranging pilot trial to determine the efficacy and safety of a preoperative infusion of sodium bicarbonate on acidosis, compared with placebo among women with obstructed labour (OL).

Justification

Undertaking a placebo-controlled, dose-ranging pilot trial shall establish a universal safe and effective dose of sodium bicarbonate for use to correct the acidosis among women with obstructed labour. Our results will inform the design of a full-scale effectiveness phase III trial to determine the effect of this preoperative infusion on maternal and perinatal outcomes. Furthermore, this information will facilitate the inclusion of sodium bicarbonate infusion in the standard preoperative preparation for women with obstructed labour in a low resource setting.

Objectives

General objective

To determine the efficacy and safety of a preoperative infusion of sodium bicarbonate on pH and lactate levels (metabolic acidosis) among women with obstructed labour.

Specific objectives

1. To determine the efficacy of a preoperative infusion of sodium bicarbonate on acidosis, compared with placebo among women with obstructed labour (OL).
2. To determine the safety of a preoperative infusion of sodium bicarbonate compared with placebo among women with obstructed labour (OL).

Hypothesis

We hypothesize that a higher dose of bicarbonate can safely lower the lactate levels (metabolic acidosis) by at least 20%.

Methods and materials

Study design

We will conduct a dose-finding phase III, randomized, double-blind, placebo-controlled, parallel-group trial.

Study setting

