We will recruit 280 participants; 70 in each of the four arms. Wiberg-Itzel et al [2] observed mean umbilical artery pH 7.23 (SD 0.07) in the non-intervention group. With our sample size, we will have 80% power (significance level 0.05) to detect mean pH changes of 0.04 and above in each arm. We are interested in detecting an effect size of 0.2 and above, which we deem to be a moderate effect size. The total sample size needed to detect a between-factor mean effect size of 0.2, by repeated measures analysis of variance (ANOVA) with a type 1 error margin of 5%, across 4 groups with 5 repeated measurements; was 224 at a power of 91%. Assuming a 20% loss to follow up in our study; we will need 280 participants (70 in each of the 4 groups). The sample size was calculated using G* Power software version 3.1 using the test family for the F test, and the statistical test for ANOVA repeated measures, between factor analysis & within-between interaction [10]. Therefore, our sample size will also be sufficient to detect a within and between-subject interaction (intervention and time interaction) with a power of 99%. To obtain these estimates, we will construct an interaction term between the intervention and the time variable. We are confident that we shall be able to accrue this number of participants in a period of six calendar months, on the basis of our experience working in the same hospital [7]. In order to detect a change in maternal pH, a minimum of two measurements are needed from a participant. However, with improvement of obstetric care, many women deliver within 30 minutes of taking the baseline measurements and hence no second measurement is obtained. To account for this form of right censoring, we have inflated our sample size by 192 participants to ensure that we have at least 280 women with at least two pH measurements. We will recruit 472 participants; 118 in each of the four arms.

Outcome variables

The primary outcome measure will be the mean change in maternal pH from baseline in each group. The secondary outcomes will include, mean pH and lactate in maternal and umbilical blood, early neonatal death, safety (side effects) of sodium bicarbonate, primary PPH, sepsis and death. Furthermore, the plasma concentrations of HCO₃ levels will be measured as well to accurately estimate the required dose.

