Data analysis plan

Data will be analyzed using Stata version 17.0 (StataCorp; College Station, TX, USA). We will describe categorical variables as proportions and compare them with chi-squared tests or Fischer's exact tests as appropriate. We will describe continuous variables as means (SD) OR medians (IQR) and compare them with t tests or Mann-Whitney U tests as appropriate. Our analysis will be by intention to treat. To determine the safety of sodium bicarbonate infusion, we will compare the incidence of side effects in each arm and report risk differences.

For the primary outcome of acidosis (pH and lactate) between-subjects repeated measures ANOVA will be conducted. We will also conduct within-subject interaction repeated measures ANOVA to assess for differences in the rate of change of pH between the groups.

We will use histograms, P-P plots, k-density, and Q-Q to assess the distribution of normality of continuous outcomes. In case the distribution of normality is not met; we shall transform our data and this decision will be guided by Stata's *gladder* command that shows various transformation options.

All analyses will be followed by a Bonferroni posthoc test for multiple comparisons, a Friedman test to compare rates of change between the various groups, and a Mauchly's test of Sphericity to check for equal variance among the combinations of the various groups. We will use Margins and Margins plots to obtain marginal means and graphical descriptions of the interaction between various groups and time.

Data Monitoring

Independent Data Monitoring Committee (IDMC)

An independent data monitoring committee (IDMC) will be appointed consisting of 3 members: a statistician, an obstetrician/gynaecologist, and a paediatrician. They will operate according to the IDMC charter, which will be developed with the members. IDMC will be encouraged to follow the recommendations of the international DAMOCLES group for IDMC activities.[12] The IDMC will monitor the trial once with a focus on issues relating to the quality of trial conduct, such as overall and site-specific rates of recruitment, adherence to trial interventions, visit schedules, losses to follow-up, and administrative and safety data. It will review administrative and safety data approximately every three months. The treatment groups will be masked in the IDMC reports.

Interim analyses and stopping guidelines

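### The sample size is not tied to maternal pH change or to the hypothesised 20% lactate fall, so the printed 91% should not be read as power for that hypothesis

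*Combined protocol and SAP*

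**What the plan says.** All references are to the combined protocol and SAP.

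- **Sample size estimation and sampling.** For pH, the plan cites a study that "observed mean umbilical artery pH 7.23 (SD 0.07) in the non-intervention group", and from this claims 80% power for a change of 0.04 with 70 women per arm. It then turns to a generic effect: "We are interested in detecting an effect size of 0.2 and above, which we deem to be a moderate effect size". The calculation is for "repeated measures analysis of variance (ANOVA) with a type 1 error margin of 5%, across 4 groups with 5 repeated measurements", and the total "was 224 at a power of 91" per cent. Allowing for 20% loss gives 280. Recruitment is raised to 472 so that at least 280 women have two or more pH values.
- **Hypothesis.** "We hypothesize that a higher dose of bicarbonate can safely lower the lactate levels (metabolic acidosis) by at least 20" per cent. The Introduction states a similar hypothesis that also names pH.
- **Introduction.** In 477 women with obstructed labour in the earlier trial, 61% had lactate above 4.8 mmol/L, "with a median capillary blood lactate level of 6.9 (3.4–13) mmol/L". The plan does not say what the bracketed interval is.
- **Status of lactate.** The opening Methods summary puts lactate in the primary outcome, and so does the Data analysis plan: "For the primary outcome of acidosis (pH and lactate) between-subjects repeated measures ANOVA will be conducted". Outcome variables names change in maternal pH as primary and lists lactate as secondary.

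**The concern.** A sample size should start from the difference the trial wants to detect and the variability of the endpoint on which it will be measured. Here the only SD describes fetal blood at one time, whereas the endpoint is a maternal change from baseline. The value f = 0.2 is derived from no pH or lactate difference, and the 20% never enters the calculation.

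The trial is meant to identify a usable dose and to inform a larger trial. If the only repeated-measures powers in print are 91% and 99%, a non-significant lactate result may be taken as evidence that these doses do not work. The design may in fact have had little chance of showing the fall it hypothesised.

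**Working it through.** **1. The plan's own figure.** For the between-factor test, λ = N·f²·m / (1 + (m−1)ρ), with 3 and N−4 degrees of freedom. Inputs from the plan are N = 224, f = 0.2, m = 5, 4 groups and α = 0.05. The correlation ρ is not stated; 0.5 is assumed. λ = 224 × 0.04 × 5/3 = 14.93, and power is 0.911. The 91% is reproduced. At ρ = 0.7 it would be 83%, and at 0.9 it would be 74%. The interaction routine at ρ = 0.5 gives more than 0.99, in line with the printed 99%. Dropout: 224/0.8 = 280.

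**2. What a 20% lactate fall is in units of f.** A percentage fall is a shift on the log scale. Assume that 3.4–13 is an interquartile range and that lactate is log-normal.

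- SD(log) = ln(13/3.4)/1.349 = 0.994.
- Standardised difference = −ln(0.8)/0.994 = 0.2231/0.994 = 0.224.
- Check on the assumption: P(lactate > 4.8) = Φ[ln(6.9/4.8)/0.994] = 64%, against the stated 61%.

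f is 0.224 times the SD of the arm-mean pattern, where 0 is placebo level and 1 is the full fall.

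| Pattern of the four arms | f | Power, N = 224 | Power, N = 280 | Fall that equals f = 0.2 |
|---|---|---|---|---|
| 0, ½, ½, 1 | 0.079 | 22% | 27% | 43% |
| 0, ⅓, ⅔, 1 | 0.084 | 24% | 29% | 41% |
| 0, 1, 1, 1 | 0.097 | 31% | 39% | 37% |

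These use the routine of step 1 with ρ = 0.5; for the first row at N = 224, λ = 224 × 0.079² × 5/3 ≈ 2.35. Over ρ from 0.3 to 0.9 the range is 15–42% at N = 224 and 18–51% at N = 280. Two arms at placebo level and two at the full fall (f = 0.112) would give 41% and 50% at ρ = 0.5. All figures assume five post-dose values per woman and a constant fall over them.

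**3. Using the baseline value.** With equal correlations, the variance of the mean of five post-dose values, relative to a single value, is:

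- unadjusted: (1+4ρ)/5;
- change from baseline: (1+4ρ)/5 − 2ρ + 1;
- baseline as covariate: (1+4ρ)/5 − ρ².

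With λ = N·f²/variance, N = 280 and the three tabulated patterns:

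| ρ | Unadjusted | Change from baseline | Baseline as covariate |
|---|---|---|---|
| 0.5 | 27–39% | 27–39% | 44–62% |
| 0.7 | 22–31% | 43–61% | 55–74% |
| 0.9 | 18–26% | 91–98% | 93–99% |

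For the covariate column the variance is 0.35, 0.27 and 0.11 respectively.

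**4. pH.** Two-sample t test, 70 per arm, difference 0.04, two-sided 0.05, unadjusted. If 0.07 were the SD of maternal pH at one time, the SD of change would be 0.07·√(2(1−ρ)), which is 0.070, 0.083 and 0.099 at ρ = 0.5, 0.3 and 0. The noncentrality is (0.04/SD)·√35 = 3.38, 2.85 and 2.39, and power is 92%, 81% and 66%. The printed 80% holds up to an SD of about 0.084.

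**The case against.** The strongest reply is that nothing printed is miscalculated. That is right. The 91% is stated for f = 0.2 and is never claimed for lactate, and 80% for a pH change of 0.04 is conservative if the SD is 0.07. A reader might infer an arithmetic error, or set the low lactate figures against 91% as if they answered the same question. The documents support neither reading; what is missing is a justification.

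Second, Outcome variables makes lactate secondary. If that section governs, the lactate power concerns a secondary endpoint. This also stands, but the Hypothesis names lactate and the Data analysis plan treats it as primary. The pH side has the same gap, since no maternal SD is used there either.

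Third, the lactate figures are not fixed by the documents. They need an unlabelled interval read as an interquartile range, an assumed correlation, a chosen pattern of arm means and a baseline spread from an earlier cohort. The exclusion of women with bicarbonate above 22 mmol/L may narrow that spread. As an illustration only, if it acted like restricting entry to lactate above 4.8, the log SD would be about 0.67 and unadjusted power at N = 280 would be 55–74% (ρ = 0.5). Analysing change with a correlation of 0.9 would give 91–98%. So a reader might infer that a true 20% fall would be missed two times in three, but the documents do not establish that. The interquartile reading is nevertheless the better one. A full range (SD roughly 1.6–2.4 mmol/L) would give at least 86% power pairwise, but it fits poorly with 61% above 4.8 mmol/L.

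**Conclusion.** The concern holds as a missing link between the sample size and the trial's own endpoints. The SD of 0.07 comes from cord blood, f = 0.2 comes from no clinical difference, and the 20% hypothesis is absent from the calculation.

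Under the interquartile reading, log-normality, ρ = 0.5 and the three tabulated patterns, the unadjusted between-subjects test has about 22–31% power at 224 women and 27–39% at 280 for a 20% lactate fall. An f of 0.2 would correspond to a fall of 37–43%. With another correlation, a narrower spread or use of the baseline value, power could be much higher. It therefore has to be shown as a range, and the documents do not support a flat statement that the trial is underpowered. The pH claim is sound at an SD of 0.07, but no section supports that value for maternal change.

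**What to change.** Keep the sample size.

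1. **Data analysis plan.** Analyse post-dose log lactate with baseline log lactate as covariate, and pH with baseline pH. Report each dose's lactate ratio to placebo with a 95% confidence interval. State that a non-significant lactate result will not be read as no effect unless the interval excludes a 20% fall, that is, lies wholly above a ratio of 0.80.
2. **Sample size section, lactate.** Say that 91% applies to f = 0.2 only. Give power for the baseline-adjusted lactate analysis as a range with its assumptions: at 280 women and a log SD of 0.99, about 44–62% at ρ = 0.5, 55–74% at 0.7 and 93–99% at 0.9. State what the 3.4–13 interval is.
3. **Sample size section, pH.** Say that 0.07 is a cord-artery stand-in, and show power over a range of SDs of maternal change (92% at 0.07, 81% at 0.083, 66% at 0.099).
4. **Outcome status.** Reconcile the Methods summary, Outcome variables and Data analysis plan on whether lactate is primary or secondary.

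The cost is wording and one model specification. Baseline lactate and pH are already scheduled in Table 1, and no more women are needed. The stated power for the lactate hypothesis becomes conditional and, at moderate correlations, less favourable.
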